**- Statistical Analysis**

Data will be coded, sorted, and analyzed using IBM SPSS Statistics version 28.0 (IBM Corp., Chicago, USA). Normality will be assessed with the Shapiro–Wilk test. Quantitative data will be expressed as mean  $\pm$  SD and compared using an independent t-test. Qualitative data will be expressed as numbers and percentages, analyzed with Chi-square or Fisher's exact test. The log-rank test will be used to compare the time to first rescue analgesia. A p-value  $< 0.05$  will be considered statistically significant.

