### **- Sample Size Calculation**

The sample size was calculated using G\*Power version 3.1.9.7 (Heinrich Heine University, Düsseldorf, Germany). The PECS II and MTP groups' mean postoperative pain scores were compared using a two-tailed independent-samples t-test. A minimum of 44 patients per group were needed based on an assumed effect size (Cohen's d) of 0.7, which was obtained from expected clinically relevant differences in VAS pain scores after 4 hours postoperatively, a power of 90% ( $1-\beta = 0.90$ ), and a two-sided alpha level of 0.05. Pilot observations and existing clinical evidence suggesting that intergroup variations in analgesic efficacy are most noticeable in the early postoperative period served as the basis for the effect size estimate.

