### **- Outcome Measures**

**Primary Outcome:** Pain intensity at rest was assessed by a 10-cm Visual Analogue Scale (VAS; 0 = no pain, 10 = worst pain imaginable) at 4 hours post-operatively.

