#### **Secondary Outcomes:**

- 1- VAS scores on admission to the PACU and at 2, 8, 12, 18, and 24 hours post-operatively.
- 2- Time to first request for rescue analgesia.
- 3- Total 24-hour consumption of rescue analgesia (intravenous nalbuphine 5 mg bolus for VAS  $\geq 4$ ).

**4-** Incidence of block-related complications (hematoma, pneumothorax, local anesthetic systemic toxicity).

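### Does the Shapiro–Wilk test with no stated consequence, followed by a t-test on 24-hour nalbuphine, call for a different analysis?

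*Combined protocol and SAP*

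**What the plan says.** The Statistical Analysis section states "Normality will be assessed with the Shapiro–Wilk test". It then says that quantitative data are to be shown as mean ± SD and "compared using an independent t-test". It gives no rule for a failed normality check and names no rank test, median or transformation. One outcome is treated separately: "The log-rank test will be used to compare the time to first rescue analgesia".

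Item 3 of the Secondary Outcomes is "Total 24-hour consumption of rescue analgesia (intravenous nalbuphine 5 mg bolus for VAS", the trigger being a score of 4 or more. The primary outcome is a resting pain score at 4 hours: "Pain intensity at rest was assessed by a 10-cm Visual Analogue Scale". The Sample Size Calculation section rests on the same test as the analysis section: "mean postoperative pain scores were compared using a two-tailed independent-samples t-test", with an "assumed effect size (Cohen's d) of 0.7", 90% power and two-sided alpha of 0.05, giving 44 per group.

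**The concern.** A normality test that leads nowhere invites two readings. Either it is idle, or the analyst will act on it by a rule that nobody has written down. On the second reading, the test for the primary outcome could be chosen after seeing the data.

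Nalbuphine adds a more specific worry. The total can only be 0, 5, 10, 15 mg and so on, and a patient who never reaches the trigger scores zero. Non-normality is therefore foreseeable, and mean ± SD may describe the data badly. The t-test may also waste power. If bolus counts have extra zeros and the arms differ mainly in how many, simulated power at 44 per arm is 14–31% for the t-test against 22–41% for the rank-sum test. At stake would be the opioid-sparing result, which readers need in order to interpret pain scores taken under rescue.

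**Working it through.** **The plan's own figure.** With d = 0.7, two-sided alpha 0.05 and power 0.90, the normal approximation gives n = 2(1.960 + 1.282)² / 0.7² = 42.9, so 43 per group. The exact t calculation gives 43.87, so 44, with power 90.1%. The stated 44 reproduces, and it is a t-test calculation.

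**Primary outcome.** Take scores rounded to whole numbers on 0–10, means 3 and 2.02 and SD 1.4 (assumed), so d = 0.98/1.4 = 0.7. Simulated power is 88.5% for the t-test and 87.4% for the rank-sum test. Nothing is gained by switching.

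**Nalbuphine: validity.** The protocol gives no distribution, share of zeros or effect size for this outcome, so every distribution below is an assumption. Under the null, with Poisson, negative binomial, hurdle (a share of zeros, then one or more boluses) and heavy-tailed counts, the t-test rejected in 4.0–4.9% of trials.

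**Nalbuphine: power.** 44 per arm, 10,000 trials per row, two-sided 0.05:

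| Assumed bolus counts | t-test | rank-sum |
|---|---|---|
| Poisson, mean 1 v 0.5 | 77% | 74% |
| Poisson, mean 3 v 2 | 84% | 82% |
| Negative binomial, 1.5 v 0.7 (k = 1) | 69% | 59% |
| Negative binomial, 2 v 0.7 (k = 0.5) | 77% | 64% |
| Hurdle, 40% zeros in both, mean 2.5 v 1.5 among the rescued | 59% | 34% |
| Hurdle, 30% v 60% zeros, mean 1.5 among the rescued in both | 65% | 75% |
| Hurdle, 50% v 75% zeros, same amounts | 57% | 66% |
| Heavy tail, 40% zeros in both | 28% | 16% |
| Heavy tail, 20% v 50% zeros | 36% | 71% |

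Two t-test rows can be checked by hand, in boluses, using power ≈ Φ(difference/SE − 1.988), where 1.988 is the t critical value on 86 degrees of freedom.

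- Poisson 1 v 0.5: SE = √((1 + 0.5)/44) = 0.185; 0.5/0.185 = 2.71; Φ(0.72) = 76%.
- Hurdle with equal zeros: means 0.6 × 2.5 = 1.5 and 0.6 × 1.5 = 0.9. Variances are 0.6(1.5 + 2.5²) − 1.5² = 2.40 and 0.6(0.5 + 1.5²) − 0.9² = 0.84. SE = √(3.24/44) = 0.271; 0.6/0.271 = 2.21; Φ(0.22) = 59%.

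The pattern is clear. The t-test does better when the amounts differ. The rank-sum test does better when only the share of zeros differs.

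**The rank-based estimate.** The natural companion to a rank-sum test is the Hodges–Lehmann shift, the median of all between-arm differences. Suppose extra zeros of 70% v 45% and negative binomial boluses for the rest (mean 2, k = 2). The negative binomial itself gives zero with probability (2/(2 + 2))² = 0.25. The arm with fewer zeros then has 0.45 + 0.55 × 0.25 = 0.59 at zero, and the other has more. Fewer than half of the paired differences can be positive, and fewer than half negative, so the true shift is 0 mg although the means differ. Across such scenarios (three pairs of zero shares, k = 1, 2 and 50) the estimate was exactly 0 mg in 70–99.8% of simulated trials.

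**Description.** Take half the patients at zero and a mean of 1.5 boluses among the rest. The mean is 0.75 boluses (3.75 mg), the variance 0.5(0.5 + 1.5²) − 0.75² = 0.81, and the SD 0.90 boluses (4.5 mg). The SD exceeds the mean, so mean ± SD alone does give an awkward picture.

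**The case for a change.** The strongest case for a change does not need the power claim. If pain scores are recorded in whole numbers, Shapiro–Wilk would reject in 70–100% of samples through rounding alone; if continuous, in about 4–36% (assumed means 2–4, SD 1.5). A failed check on the primary outcome is thus quite possible, and the protocol does not say what follows. For nalbuphine, the t-test and rank-sum test gave different significance verdicts in 8–15% of simulated trials, which is the room that an unwritten rule would leave. Two sentences would close the gap.

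The silence is real, and so is the awkwardness of mean ± SD. But the text names one test for quantitative data, attaches no condition and offers no alternative, and the sample size section names the same test for the 4-hour score. An analyst who follows the protocol runs the t-test; a switch would be a visible departure from it. The disagreement between tests matters only if someone departs in that way. The concern also cannot cover every quantitative outcome, because time to first rescue goes to the log-rank test, which already reflects whether a patient needed rescue at all.

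**Conclusion.** The concern does not call for a change. Followed as written, the plan gives valid tests: type I error is at or just under 5% at 44 per arm. A general loss of power is not shown. Its direction turns on an unstated distribution, and in the scenarios tried it ranged from a 25-point advantage for the t-test to a 35-point advantage for the rank-sum test. Moving to ranks would also exchange a mean difference in mg, which readers can interpret as opioid sparing, for a shift that is often exactly zero when zeros are common. That is a trade-off with no clear gain.

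The idle normality test is a small gap in wording. Analysts ordinarily fill it by running the named test and, for a stepped total, showing the median, the quartiles and the proportion given any rescue beside the mean. None of that alters a planned comparison.

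This rests on two assumptions: that zeros occur, which is inferred from dosing only at a pain score of 4 or more, and that the distributions tried span the plausible range. An extremely heavy tail combined with a difference in zeros is the one setting where the t-test would do markedly worse, and nothing in the protocol points to it.

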## **2. AIM / OBJECTIVES:**

This study aims to compare the analgesic efficacies of the modified pectoral plane block (PECS II) and the midpoint transverse process to pleura block (MTP), after modified radical mastectomy (MRM) surgery.

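### Does the plan need an effect estimate beside the log-rank test for time to first rescue?

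*Combined protocol and SAP*

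**What the plan says.** The Statistical Analysis section is a single paragraph. For continuous data it states "Quantitative data will be expressed as mean" ± SD, with an independent t-test. Categorical data are given as counts and percentages with a chi-square or Fisher's exact test. Time to first rescue has its own sentence: "The log-rank test will be used to compare the time to first rescue analgesia". Significance is judged at p < 0.05. No hazard ratio, median, restricted mean or confidence interval is named for any outcome.

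Under Secondary Outcomes, the second item is "Time to first request for rescue analgesia" and the third is "Total 24-hour consumption of rescue analgesia". The last planned VAS assessment is also at 24 hours. How to treat a patient who never asks for rescue is not written down.

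The Sample Size Calculation section gives the effect only in standardised form, "based on an assumed effect size (Cohen's d) of 0.7". It describes the source in words, "which was obtained from expected clinically relevant differences in VAS pain scores after 4 hours postoperatively", without an SD or a difference in centimetres.

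**The concern.** The trial compares the analgesic efficacy of two blocks, and the time a block lasts before rescue is a direct measure of that. A log-rank test says whether the two curves differ, not by how much. For the VAS scores, rescue consumption and complications, a reader can rebuild the difference and its interval from the means, SDs or counts with 44 per arm. Rescue time lacks this safeguard if only a p-value is printed.

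Two further worries follow. With no summary named, one could be picked after the data are seen. With no censoring rule, someone might average only the rescued patients and so drop those with the best pain relief. Separately, d = 0.7 without an SD leaves the reader unable to judge in centimetres whether the assumed difference is clinically relevant.

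**Working it through.** **1. The plan's own figure.** Inputs from Sample Size Calculation: d = 0.7, "a two-sided alpha level of 0.05", power 90%, 1:1 allocation. The noncentral t calculation gives 43.87 per group, rounded up to 44, with power 0.901 at 44. The stated size is right. Only d enters the calculation, so the missing SD cannot affect n. It affects only the translation to centimetres, 0.7 × SD: 0.7 cm at SD 1.0 and 1.75 cm at SD 2.5 (assumed SDs).

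**2. Primary outcome.** The 95% interval half-width is t(0.975, 86) × √(2/44) = 1.988 × 0.2132 = 0.424 SD. With a mean and SD per arm, the reader can compute the difference and its interval, so nothing is lost.

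**3. What a log-rank p-value conveys.** With equal arms and D patients rescued, ln(HR) ≈ 2z/√D with standard error 2/√D. Take p = 0.01, so z = 2.576. The documents give no rescue rate, so D is an assumption.

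| D | HR = exp(2 × 2.576/√D) | 95% CI |
|---|---|---|
| 22 | 3.00 | 1.30 to 6.92 |
| 44 | 2.17 | 1.20 to 3.93 |
| 66 | 1.89 | 1.16 to 3.05 |
| 88 | 1.73 | 1.14 to 2.63 |

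An approximate hazard ratio and interval can therefore be recovered from the p-value and one count, the number rescued. The scale in hours cannot.

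**4. The same evidence in hours.** Assume exponential times and censoring at 24 h. If a proportion p is rescued by 24 h in the better arm, its cumulative hazard is L = −ln(1 − p); the other arm has HR × L. Mean rescue-free time over 24 h is 24 × (1 − e^(−L))/L. The z expected from the log-rank test is about ln(HR) × √D/2, with D = 44 × (sum of the two proportions).

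| Rescued | HR | Mean rescue-free time, h | Difference, h | Expected z |
|---|---|---|---|---|
| 20% vs 40% | 2.30 | 21.51 vs 18.77 | 2.7 | 2.14 |
| 30% vs 53% | 2.10 | 20.19 vs 16.89 | 3.3 | 2.24 |
| 50% vs 75% | 2.00 | 17.31 vs 12.98 | 4.3 | 2.57 |
| 90% vs 98% | 1.75 | 9.38 vs 5.85 | 3.5 | 2.55 |
| 99% vs about 100% | 1.73 | 5.16 vs 3.01 | 2.1 | 2.56 |
| nearly all, early (medians 1.8 vs 1.0 h) | 1.73 | 2.60 vs 1.50 | 1.1 | 2.57 |

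The last four rows all sit near p = 0.01, yet the differences run from 1.1 to 4.3 h. The first two rows give weaker evidence on average. Simulated trials from the 20% vs 40% and 30% vs 53% settings that happen to reach p near 0.01 average about 3.4 h and 3.9 h, but these are selected for a larger contrast than the nominal rates imply.

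**5. Would naming a hazard ratio settle it?** Not in hours. In the last two rows the same hazard ratio, 1.73, goes with both 2.1 h and 1.1 h. Only the curves or a restricted mean show the difference in time.

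**6. Censoring.** A log-rank test needs a time and a status for every patient. Rescue use is counted over 24 hours, so the natural entry for a patient without rescue is 24 h, censored. That is one common cut-off for both arms, so it introduces no bias between them.

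**The case for a change.** The strongest case for a change is that the remedy costs almost nothing. One sentence would fix the censoring time and name a summary in advance, with no effect on patients, alpha, power or n. The general sentence on means and SDs does not clearly cover rescue time, because it is tied to a t-test while rescue time has its own test. A plain mean is also poorly defined once anyone is censored. And the spread of 1.1 to 4.3 h is large in a 24-hour window.

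Much of this stands as reporting advice. The paper would be better for Kaplan-Meier curves, the number never rescued in each arm, and a restricted mean difference over 24 h with its interval. It does not show a defect in the plan, because the pre-specified test answers whether the arms differ and remains correct whichever summary is printed beside it. Nothing in the plan says that only a p-value will be published; that reading rests on the silence of a one-paragraph section. The freedom to choose a descriptive summary is real, but it cannot alter the test result on a secondary outcome.

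**Conclusion.** No change is needed. The plan leaves a reporting detail unstated for one secondary outcome, and ordinary practice fills it: 24 h is the evident censoring time, and Kaplan-Meier curves normally accompany a log-rank test. If a bare p-value were printed, the cost would be interpretive: p near 0.01 could mean about 1.1 h or about 4.3 h of extra rescue-free time. That range assumes exponential times, 24-hour censoring and rescue rates that the documents do not give. The primary comparison, the significance level, the 44 per group and every planned test stand. The d = 0.7 remark has no bearing on the calculation, and for the 4-hour VAS the interval can be recovered from what is already planned.
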